9.1.6 Early study termination by the sponsor

The study can be terminated by Novartis at any time for any reason. This may include reasons related to the benefit/ risk assessment of participating in the study, practical reasons (including slow enrollment), or for regulatory or medical reasons. In taking the decision to terminate, Novartis will always consider the subject welfare and safety. Should early termination be necessary, subjects must be seen as soon as possible (provide instruction for contacting the subject, when the subject should stop taking drug, when the subject should come for a final visit) and treated as a prematurely withdrawn subject. The investigator may be informed of additional procedures to be followed in order to ensure that adequate consideration is given to the protection of the subject's interests. The investigator or sponsor depending on the local regulation will be responsible for informing IRBs/IECs of the early termination of the trial.

9.2 Study completion and post-study treatment

Study completion is defined as when the last patient finishes their Study Completion visit, and any repeat assessments associated with this visit have been documented and followed-up appropriately by the Investigator, or in the event of an early study termination decision, the date of that decision.

Each patient will be required to complete the study in its entirety and thereafter no further study treatment will be made available to them, unless required by local regulations.

10 Safety monitoring and reporting

10.1 Definition of adverse events and reporting requirements

10.1.1 Adverse events

An adverse event (AE) is any untoward medical occurrence (e.g., any unfavorable and unintended sign [including abnormal laboratory findings], symptom or disease) in a subject or clinical investigation subject after providing written informed consent for participation in the study. Therefore, an AE may or may not be temporally or causally associated with the use of a medicinal (investigational) product.

The investigator has the responsibility for managing the safety of individual subject and identifying adverse events.

Novartis qualified medical personnel will be readily available to advise on trial related medical questions or problems.

The occurrence of adverse events must be sought by non-directive questioning of the subject at each visit during the study. Adverse events also may be detected when they are volunteered by the subject during or between visits or through physical examination findings, laboratory test findings, or other assessments.

Adverse events must be recorded in the Adverse Events CRF under the signs, symptoms or diagnosis associated with them, accompanied by the following information (as far as possible) (if the event is serious refer to [Section 10.1.2](#)):

1. the severity grade
 - mild: usually transient in nature and generally not interfering with normal activities
 - moderate: sufficiently discomforting to interfere with normal activities
 - severe: prevents normal activities
2. its relationship to the study treatment. If the event is due to lack of efficacy or progression of underlying illness (i.e., progression of the study indication) the assessment of causality will usually be 'Not suspected'. The rationale for this guidance is that the symptoms of a lack of efficacy or progression of underlying illness are not caused by the trial drug, they happen in spite of its administration and/or both lack of efficacy and progression of underlying disease can only be evaluated meaningfully by an analysis of cohorts, not on a single subject
3. its duration (start and end dates) or if the event is ongoing, an outcome of not recovered/not resolved must be reported.
4. whether it constitutes a SAE (see [Section 10.1.2](#) for definition of SAE) and which seriousness criteria have been met
5. action taken regarding with the study treatment.

All adverse events must be treated appropriately. Treatment may include one or more of the following:

- Dose not changed
 - Dose reduced/increased
 - Drug interrupted/withdrawn
6. its outcome:
 - a. not recovered/not resolved;
 - b. recovered/resolved;
 - c. recovering/resolving,
 - d. recovered/resolved with sequelae;
 - e. fatal, or
 - f. unknown.

Conditions that were already present at the time of informed consent should be recorded in medical history of the subject.

Adverse events (including lab abnormalities that constitute AEs) should be described using a diagnosis whenever possible, rather than individual underlying signs and symptoms.

Adverse event monitoring should be continued until the EoS visit.

Once an adverse event is detected, it must be followed until its resolution or until it is judged to be permanent (e.g., continuing at the end of the study), and assessment must be made at each visit (or more frequently, if necessary) of any changes in severity, the suspected relationship to the interventions required to treat it, and the outcome.

Information about adverse drug reactions for the investigational drug can be found in the Investigator Brochures (IBs).

Any new information regarding the safety profile of the medicinal product that is identified between IB updates will be communicated as appropriate, for example, via an Investigator Notification. New information might require an update to the informed consent and has then to be discussed with the subject.

Abnormal laboratory values or test results constitute adverse events only if they fulfill at least one of the following criteria:

- they induce clinical signs or symptoms
- they are considered clinically significant
- they require therapy

10.1.2 Serious adverse events

An SAE is defined as any adverse event [appearance of (or worsening of any pre-existing)] undesirable sign(s), symptom(s) or medical condition(s)) which meets any one of the following criteria:

- fatal
- life-threatening:
life threatening in the context of a SAE refers to a reaction in which the subject was at risk of death at the time of the reaction; it does not refer to a reaction that hypothetically might have caused death if it were more severe (please refer to the [ICH-E2D Guidelines 2004](#)).
- results in persistent or significant disability/incapacity
- constitutes a congenital anomaly/birth defect
- requires inpatient hospitalization or prolongation of existing hospitalization, unless hospitalization is for:
 - routine treatment or monitoring of the studied indication, not associated with any deterioration in condition
 - elective or pre-planned treatment for a pre-existing condition that is unrelated to the indication under study and has not worsened since signing the informed consent
 - social reasons and respite care in the absence of any deterioration in the subject's general condition
 - treatment on an emergency outpatient basis for an event not fulfilling any of the definitions of a SAE given above and not resulting in hospital admission
- is medically significant, e.g. defined as an event that jeopardizes the subject or may require medical or surgical intervention to prevent one of the outcomes listed above

Medical and scientific judgment should be exercised in deciding whether other situations should be considered serious reactions, such as important medical events that might not be immediately life threatening or result in death or hospitalization but might jeopardize the subject or might require intervention to prevent one of the other outcomes listed above. Such events should be considered as “medically significant”. Examples of such events are intensive treatment in an emergency room or at home for allergic bronchospasm, blood dyscrasias or convulsions that do not result in hospitalization or development of dependency or abuse (please refer to the [ICH-E2D Guideline 2004](#)).

All malignant neoplasms will be assessed as serious under “medically significant” if other seriousness criteria are not met.

Any suspected transmission via a medicinal product of an infectious agent is also considered a serious adverse reaction.

All reports of intentional misuse and abuse of the product are also considered serious adverse event irrespective if a clinical event has occurred.

10.1.3 SAE reporting

To ensure subject safety, every SAE, regardless of causality, occurring after the subject has provided informed consent and until 30 days after the last study visit must be reported to Novartis safety immediately, without undue delay, but under no circumstances later than within 24 hours of obtaining knowledge of the events (Note: If more stringent, local regulations regarding reporting timelines prevail). Detailed instructions regarding the submission process and requirements are to be found in the investigator folder provided to each site.

1. **Screen Failures.** SAEs occurring after the subject has provided informed consent until the time the subject is deemed a Screen Failure must be reported to Novartis.
2. **Randomized OR Treated Subjects.** SAEs collected between time subject signs ICF until the subject has discontinued or stopped the study. All follow-up information for the SAE including information on complications, progression of the initial SAE and recurrent episodes must be reported as follow-up to the original episode within 24 hours of the investigator receiving the follow-up information. An SAE occurring at a different time interval or otherwise considered completely unrelated to a previously reported one must be reported separately as a new event.

All follow-up information for the SAE including information on complications, progression of the initial SAE and recurrent episodes must be reported as follow-up to the original episode immediately, without undue delay, but under no circumstances later than within 24 hours of the Investigator receiving the follow-up information (Note: If more stringent, local regulations regarding reporting timelines prevail). An SAE occurring at a different time interval or otherwise considered completely unrelated to a previously reported one must be reported separately as a new event.

If the SAE is not previously documented in the Investigator’s Brochure or Package Insert (new occurrence) and is thought to be related to the study treatment, a CMO & PS Department associate may urgently require further information from the investigator for health authority reporting. Novartis may need to issue an Investigator Notification (IN) to inform all

investigators involved in any study with the same study treatment that this SAE has been reported.

Suspected Unexpected Serious Adverse Reactions (SUSARs) will be collected and reported to the competent authorities and relevant ethics committees in accordance with EU Guidance 2011/C 172/01 or as per national regulatory requirements in participating countries.

Any SAEs experienced after the 30-day period after the last study visit should only be reported to Novartis Safety department if the investigator suspects a causal relationship to study treatment.

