12.5.2 Safety endpoints

For all safety analyses, the safety set will be used. All listings and tables will be presented by period and treatment group.

Safety summaries (tables, figures) include only data from the on-treatment period with the exception of baseline data which will also be summarized where appropriate (e.g., change from baseline summaries). In addition, a separate summary for death including on treatment and post treatment deaths will be provided. In particular, summary tables for adverse events (AEs) will summarize only on-treatment events, with a start date during the on-treatment period (*treatment-emergent* AEs).

The on-treatment period lasts from the date of first administration of study treatment until end of study (EoS).

Adverse events

All information obtained on adverse events will be displayed by treatment group and subject.

The number (and percentage) of subjects with treatment emergent adverse events (events started after the first dose of study medication or events present prior to start of double-blind treatment but increased in severity based on preferred term) will be summarized in the following ways:

1. by treatment group, primary system organ class and preferred term.
2. by treatment group, primary system organ class, preferred term and maximum severity.

Separate summaries will be provided for study medication related adverse events, death, serious adverse events, other significant adverse events leading to discontinuation and adverse events leading to dose adjustment.

The number (and proportion) of subjects with adverse events of special interest will be summarized by treatment group. A subject with multiple adverse events within a primary system organ class is only counted once towards the total of the primary system organ class.

Vital signs

All vital signs data will be listed by treatment group, subject, and visit and if ranges are available, abnormalities will be flagged. Summary statistics (e.g., change from baseline and shift tables) will be provided by treatment group and visit.

12-lead ECG

All ECG data will be listed by treatment group, subject and visit, abnormalities will be flagged. Summary statistics will be provided by treatment group and visit.

1. PR, QRS, QT, QTcF, and RR intervals will be obtained from 12-lead ECGs for each subject during the study. ECG data will be read and interpreted (/locally).

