The number and percentage of patients with clinically notable laboratory results after baseline will be presented.

Adverse events

All information obtained on adverse events will be displayed by treatment and participant.

The number and percentage of patients with adverse events will be tabulated by body system and preferred term with a breakdown by period and treatment. A patient with multiple adverse events within a body system is only counted once towards the total of this body system and treatment. Separate tables and listings will be presented indicating event severity and study drug relationship.

The on-treatment/ treatment emergent period lasts from date of first administration of study treatment until end of study (EoS). Summary tables for adverse events (AEs) will summarize only on-treatment events, with a start date during the on-treatment period (treatment emergent AEs).

For the legal requirements of ClinicalTrials.gov and EudraCT, two required tables on <on-treatment/treatment emergent> adverse events which are not serious adverse events with an incidence greater than 5% and on <on-treatment/treatment emergent> serious adverse events and SAE suspected to be related to study treatment will be provided by system organ class and preferred term on the safety set population.

If for a same patient, several consecutive AEs (irrespective of study treatment causality, seriousness and severity) occurred with the same SOC and PT:

- a single occurrence will be counted if there is ≤ 1 day gap between the end date of the preceding AE and the start date of the consecutive AE
- more than one occurrence will be counted if there is > 1 day gap between the end date of the preceding AE and the start date of the consecutive AE.

For occurrence, the presence of at least one SAE / SAE suspected to be related to study treatment / non-SAE has to be checked in a block e.g., among AE's in a ≤ 1 day gap block, if at least one SAE is occurring, then one occurrence is calculated for that SAE.

The number of deaths resulting from SAEs suspected to be related to study treatment and SAEs irrespective of study treatment relationship will be provided by SOC and PT.

Injection-related Reactions

Injection-related reactions will be summarized by type of injection reaction (overall, local and systemic), by grading, and by visit. Injection-related reaction events will be listed by treatment, patient and visit/time.

Other safety evaluations

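### Protocol 10.1.3 ends SAE collection at two different points, and non-fatal SAEs in the 30 days between them fall outside the summary tables

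*Protocol*

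**What the plan says.** **Collection.** The lead sentence of protocol 10.1.3 covers every SAE, whatever its cause, "occurring after the subject has provided informed consent and until 30 days after the last study visit must be reported to Novartis safety immediately". The closing paragraph relies on the same limit: "Any SAEs experienced after the 30-day period after the last study visit should only be reported to Novartis Safety department", and then only if the investigator suspects a causal link. Between these, item 2 sets the rule for randomised or treated patients: "SAEs collected between time subject signs ICF until the subject has discontinued or stopped the study". Protocol 10.1.1 continues general adverse event monitoring up to the EoS visit.

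**Tables.** Protocol 12.5.2 states: "Safety summaries (tables, figures) include only data from the on-treatment period with the exception of baseline data". It ends that period at EoS. Its one exception after that point is a separate summary of deaths, which includes post-treatment deaths. SAP 8.2 agrees: "The on-treatment/ treatment emergent period lasts from date of first administration of study treatment until end of study (EoS". It counts only events that start in this period, and the SAE tables for the public registries use the same restriction.

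**Listings.** Both 12.5.2 and SAP 8.2 provide for all adverse event information obtained to be displayed by treatment and patient.

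**The concern.** Item 2 is the line addressed to exactly the patients who matter here. A site could apply it in good faith and stop collecting when a patient leaves, although the rest of the section makes the next 30 days mandatory. The table rule raises a separate problem: a non-fatal SAE that was correctly reported in those 30 days would not be counted in any arm-level summary.

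For a patient who completes follow-up, the tail comes long after the last dose. For a patient who leaves the study shortly after a dose, it can be the period of highest exposure. A serious infection starting a week after such a departure is the kind of event that a placebo-controlled safety comparison should count.

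**Working it through.** No sample size or error rate is involved. The check sets the provisions side by side and does date arithmetic.

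**Step 1: days covered after the last study visit**

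| Provision | End of window | Days after last visit |
|---|---|---|
| 10.1.3, lead sentence | last visit + 30 days | 30 |
| 10.1.3, closing paragraph | same limit; suspected-related SAEs only after it | 30 |
| 10.1.3, item 2 | patient has left the study | 0 if leaving coincides with the last visit |
| 12.5.2 and SAP 8.2, tables | EoS | 0 if EoS is the last visit |

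The disputed window is 30 − 0 = up to 30 days per patient, both for collection and for the tables.

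**Step 2: where the window falls relative to dosing.** The last planned dose is at Week 49, and the EoS visit for Cohort 2 is at Week 69 (protocol section 3).

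- Cohort 2 completer under item 2: (69 − 49) × 7 = 140 days after the last dose.
- The same patient under the 30-day rule: 140 + 30 = 170 days.
- Cohort 1 patient in secondary follow-up: later still, because those visits may run to 2 years after end of treatment. The 140 and 170 day figures do not apply.
- Patient whose last study visit is a dosing visit (assumed worst case): 0 days under item 2 and 30 under the lead sentence. The difference exceeds one dosing interval of 4 × 7 = 28 days.

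**Step 3: follow one event.** Suppose a non-fatal SAE starts 7 days after the last visit of a patient who left before Week 29.

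- Lead sentence: it must be reported.
- Item 2: it need not be collected.
- If it is reported: it is outside the summary tables if EoS is taken as the leaving date, but eligible for the listings.

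The visible text does not define EoS for an early leaver, so the table cut-off for this patient is itself unclear.

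**Step 4: which period would it belong to?** SAP section 5 ends the blinded period at Visit 190 (Week 29). SAP section 8 moves that visit into the open-label period for safety and summarises post-treatment follow-up with the open-label period. Neither places an event that follows an exit before Week 29. Even if the window were extended, a period rule would still be needed.

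**The case against.** The strongest reply is that item 2 is one loosely worded line against two clear statements. The lead sentence is mandatory, the closing paragraph relies on it, and suspected-related SAEs remain reportable after day 30. A careful site would report the event. This stands as far as it goes: a reader might infer that SAEs after early withdrawal are lost, and the documents do not support that. They may go uncollected where item 2 is followed. If collected, they can appear in listings, and deaths are summarised separately.

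The affected group is also narrow. Protocol 9.1.1 keeps patients who only stop treatment in the study, with visits for safety monitoring. Protocol section 8 calls those who leave for a final visit, and the time up to that visit is covered. After withdrawal of consent, 9.1.3 restricts contact and further data, so loss there comes mainly from consent and better wording would recover little. What remains is patients whose study participation ends without withdrawal of consent. Early termination by the sponsor (9.1.6) is one such route.

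A reader might also take the 10% over-recruitment allowance in 9.1.2 as a dropout rate and infer that 0.10 × 120 = 12 patients have the gap right after dosing. The allowance is not a dropout rate, and early leavers would not all leave at a dosing visit. Even 12 such patients would give 12 × 30 = 360 days, about 1 patient-year, against 120 × 196 = 23,520 days, about 64 patient-years, of planned follow-up to Week 29. Safety analysis here is descriptive, in a non-confirmatory study.

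These points limit the size of the problem. They do not remove the contradiction within 10.1.3 or bring a reported non-fatal tail SAE into the tables.

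**Conclusion.** The point holds in a limited form. One section gives the same patients two SAE end points up to 30 days apart, and both documents end the SAE summary tables at EoS, with an exception only for deaths. The consequence is possible non-collection at sites that follow item 2, and exclusion of non-fatal tail SAEs from arm-level summaries.

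The worst case, 30 days against 0 after a dose, assumes that the last study visit is a dosing visit. For the tables it also assumes that EoS for an early leaver is the leaving date, which is an inference from text that gives no definition. The number of such patients and the number of missed events cannot be derived from the documents. A difference between arms is possible but cannot be shown. This is a rule to correct because it contradicts the rest of its section; the documents do not show that the safety comparison is materially biased.

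**What to change.** - **Protocol 10.1.3:** reconcile item 2 with the 30-day limit in the lead sentence and closing paragraph.
- **Protocol and SAP:** define EoS for patients who leave the study early.
- **Protocol 12.5.2 and SAP 8.2:** extend the SAE table window to 30 days after the last study visit, or add a supplementary SAE table for that window.
- **Period rule:** assign tail SAEs of patients who leave before Week 29 to the blinded period and the randomised arm. Protocol 12.1 analyses by treatment received, so the two differ only if a patient was given the wrong treatment.

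The cost is a few sentences. No visits or procedures are added, because the 30-day duty already exists. The benefit is limited by timing: the SAP says that the CFZ533 results were final in an earlier interim report, and it applies the amendment 5 follow-up rule only to the 3 last patients. New wording cannot recover SAEs that sites did not collect. The analysis change should therefore apply to the final VAY736 report, using tail SAEs already reported. If some of these are held only in the safety database, they would have to be brought into the analysis data.
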